12.2 Management of risks associated with anemia

This trial limits the total volume drawn over each sequential 8 week period to less than 550 mL, however, if a trial subject develops anemia, they should be evaluated and treated with iron supplements if appropriate.

If the trial subject develops Grade 3 anemia, the volume of blood drawn at any visit will be kept to a minimum, i.e., may be reduced to only safety assessments, at the discretion of the investigator.

12.3 Management of risks linked to the pandemic COVID-19

Risks linked to the pandemic COVID-19 will be managed by requiring:

 Avoidance of contact with persons tested positive for SARS-CoV-2 or have an increased risk for infection during their participation in the trial.

Clinical Trial Protocol Trial number: BNT165-01 Page 82 of 82 Version: 4.0 Date: 13 FEB 2023

- Practice of social distancing and follow good practices to reduce their chances of being infected or spreading COVID-19 during their participation in the trial.
- Completion of health status checks which include symptom-directed physical examinations, vital signs assessments, and clinical laboratory tests on visit days.

Use of the Subject hotline to contact the trial site during their participation in the trial should they require guidance or should they experience any symptoms of illness. The reporting of any symptoms of illness, e.g., enhanced respiratory disease or flu-like symptoms, may trigger diagnostic measures at the discretion of the investigator.

1 SAP APPROVAL

This Statistical Analysis Plan (SAP) has been prepared, reviewed, and approved in accordance with the ICON standard operating procedure (SOP). Documentation of this process is filed in the trial master file (TMF).

2 VERSION HISTORY

Table 1: SAP Version History Summary

SAP version	Version date	Change	Rationale
1.0	14 Feb 2023	N/A	Original Version
2.0	30 May 2023	- Section 3.1: Table 2 updated	Aligned to CTP V 4.0
		- Section 3.2: Table 3 updated	Aligned to CTP V 4.0
		 Section 8.5.2: Listing for delayed local reactions added. 	Aligned to CTP V 4.0
		Section 8.5.4: Analysis period for MAAEs modified	Aligned to CTP V 4.0
		 Section 8.5.4.1: Analysis of "any solicited reactogenicity event that continues longer than 7 d post-IMP administration or is an SAE" added to safety overview table 	Clarification
		- Section 8.5.4.3: threshold of 5% deleted for analysis of non-serious AEs.	Given the small sample size per cohort, applying a threshold is not meaningful.
		Section 8.5.5: Clarification that Urinalysis will be listed only.	Clarification
		 Section 8.5.8: Addition of listing of data collected during wellbeing calls. 	Clarification
		- Section 10.4: Table 7 updated	Aligned to CTP V 4.0
3.0	08 May 2024	- Section 3.1: Removed the exploratory endpoint.	Immunogenicity endpoints analyses will not be in the CSR.
		 Section 8.1.2: Added instructions for handling the missing AE end dates. 	Clarification
		- Section 8.4: Removed the phrase regarding the immunogenicity assessment.	Immunogenicity endpoints analyses will not be in the CSR.
		- Section 8.6.1: Removed the immunogenicity endpoints analysis. Removed the subsections 8.6.1.1 and 8.6.1.2.	Immunogenicity endpoints analyses will not be in the CSR.

Page 6 of 36 Version: 3.0 Date: 08 MAY 2024

3 INTRODUCTION

This is an exploratory Phase I, randomized, observer-blind, placebo-controlled dose escalation trial evaluating the safety, tolerability and immunogenicity of an investigational RNA-based vaccine for active immunization against malaria. The results might be included in a regulatory submission. This statistical analysis plan (SAP) describes the detailed procedures for the planned statistical analyses for protocol BNT165-01 to support the completion of the Clinical Trial Report (CTR). This SAP will also include the details of the presentation and analysis of any applicable interim analyses.

The statistical analyses will be conducted by ICON clinical research using SAS® software Version 9.4 or higher.

3.1 Objectives, estimands and endpoints

The estimands and endpoints corresponding to each primary and exploratory objective are described in Table 2.

This SAP provides details on the analysis of the primary endpoints.

The analysis of exploratory endpoints is out of scope of this SAP and will be described in a different document.

Table 2: Objective, estimands and endpoints

OBJECTIVES	ESTIMANDS	ENDPOINTS
Primary objectives		
To describe the safety and tolerability of BNT165b1 vaccination in healthy adults.	 For each DL cohort: Frequency of solicited local reactions at the injection site recorded up to 7 d after each dose. Frequency of solicited systemic reactions recorded up to 7 d after each dose. Proportion of subjects with at least one AE occurring up to 28 d after each dose. Proportion of subjects with at least one MAAE occurring up to 28 d after each dose. Proportion of subjects in each cohort with at least one SAE occurring up to 24 weeks after Dose 3. 	 Solicited local reactions (pain, erythema/redness, induration/swelling) Solicited systemic reactions (vomiting, diarrhea, headache, fatigue, myalgia, arthralgia, chills, and fever) AEs SAEs MAAEs

Statistical Analysis Plan (SAP) BNT165-01

Page 7 of 36 Version: 3.0 Date: 08 MAY 2024

OBJECTIVES	ESTIMANDS	ENDPOINTS
Exploratory objectives		
To describe the humoral immune responses induced by BNT165b1 vaccination at different DLs in healthy adults.	Not applicable	Levels of antigen-specific serum and/or plasma antibodies (total IgG) measured using ELISA and/or similar assays CCI
CCI		
Abbreviations: AE = adverse ever	nt: CCI	d(s) = day; DL(s) = dose level(s);
ELISA = enzyme-linked immunos	orbent assay; lgG = immunoglobulin (E = serious adverse event.	G; MAAE = medically attended adverse event;

Page 8 of 36 Version: 3.0 Date: 08 MAY 2024

3.2 Trial design

The trial design is as shown in below Table 3.

Table 3: Trial Design

Trial Design	The BNT165 multi-antigen vaccine clinical development will begin with this First-in-Human (FIH) clinical trial, a dose escalation multi-center trial designed to assess the safety, tolerability, and exploratory immunogenicity of the vaccine component. The vaccine component assessed in this trial will be BNT165b1, a Ribonucleic acid -lipid nanoparticle (RNA-LNP) encoding for part of P. falciparum circumsporozoite protein (Pf CSP). Subsequently, multiple other vaccine components will be assessed (either individually or combinations) as well. BNT165b1 will be evaluated at three dose levels (DLs) to select a safe and tolerable dose in a 3-dose schedule. A sponsor Internal Review Committee (IRC) will be used for the BNT165-01 clinical trial.								
Trial population	his trial will enroll healthy volunteers aged 18 to 55 years with no history of previous or current malaria infection. Trial ubjects must not have received any approved or investigational malaria vaccine or have participated in a previous malaria hallenge trial. All subjects must meet the trial eligibility criteria listed in Section 5 of protocol.								
Investigational medical product(s)	Name: BNT165b1 Type: Investigational Dose: • 3 μg BNT165b1 or isotonic NaCl solution (0.9%) • 10 μg or lower BNT165b1 or isotonic NaCl solution (0.9%) • 30 μg or lower BNT165b1 or isotonic NaCl solution (0.9%) Schedule: Three (one each on Days 1, 57, and 183) injections given at each dose level. Route of administration: Intramuscular injection in the deltoid muscle of the non-dominant arm. Other injection sites may be used if necessary. Allocation to IMP: Trial subjects will be randomized 4:1 to BNT165b1: placebo using an online randomization tool.								
Treatment and trial duration	The planned trial duration for each trial subject is ~19 months (up to 4 weeks screening, ~26 weeks treatment phase, and ~52 weeks follow-up phase).								

Statistical Analysis Plan (SAP) BNT165-01

Page 9 of 36 Version: 3.0 Date: 08 MAY 2024

Planned number of patients	A total of 60 subjects are expected to enroll in the cohorts evaluating BNT165b1, such that there are 20 trial subjects for each of the cohorts as planned. Per cohort, trial subjects will be randomized 4:1, using an online randomization tool to receive either vaccine or placebo (i.e., of 20 subjects, 16 subjects and 4 subjects will receive the vaccine or placebo, respectively).
Randomization and blinding	Randomization: This is a 3-dose cohort observer-blind trial.
	Blinding: All randomized trial subjects will be blinded to their assigned trial treatments.
	The trial personnel dispensing and administering the vaccine will be unblinded, but all other trial personnel, including the principal investigator, and the subject, will be blinded.
	The investigator and any site personnel other than the unblinded dispenser/administrator must not be allowed to know the IMP assigned to any trial subject and must not be allowed to see the drug product containers. Because BNT165b1 and placebo differ in their physical appearance, the trial treatment will be provided in a manner that maintains the blinding, e.g., syringes will be masked or colored.
Other features	An IRC will provide medical oversight of trial subject safety during the conduct of this trial, with a focus on guidance, management of emergent safety issues, and decision-making as outlined in the IRC charter.

Page 10 of 36 Version: 3.0 Date: 08 MAY 2024

Dose Escalation

Dose escalation decisions to progress to the next dose level (DL) and DL modifications (i.e., dropping the DL to the previous acceptable DL or to an 'in-between' DL) will be confirmed by the IRC. Dose escalation will only continue if the safety and reactogenicity of the previous DL was considered acceptable by the IRC and no stopping/pausing rules were met.

In addition to the above triggers for dose modifications, other unplanned dose modifications, pausing (temporary halting) of trial treatment, or even discontinuation of trial treatment may be required. See Section 7.1 of protocol for guidance on criteria for such cases.

3.3 Schema (graphical representation of the trial)

Figure 1: Trial schema

M0, M2, M6 represent the dosing schedule at Days 1, 57, and 183; D7 represents IRC review after 7 days follow-up post-Dose 1.

[figure not shown]

Figure 2: The staggered dosing process for the cohorts

Page 11 of 36 Version: 3.0 Date: 08 MAY 2024

- In case of safety concerns the IRC can decide to reduce to an intermediate dose.
- b. Further dosing of subjects will proceed if the investigator considers the vaccine reactogenicity is acceptable and no stopping/pausing rules are met.
- Further opening of new cohorts will proceed if the IRC considers the vaccine reactogenicity is acceptable and no stopping/pausing rules are met.

Abbreviations: d = days; DL = dose level; h = hour(s); FIH = first-in-human; IRC = Internal Review Committee.

3.4 Schedule of activities

See Section 10.4 Appendix 4 for the schedule of activities.

4 STATISTICAL HYPOTHESES

No formal statistical hypotheses will be tested in this exploratory trial.

5 INTERIM ANALYSES AND ANALYSIS SEQUENCE

An interim analysis on adverse events, reactogenicity and immunogenicity data will be performed when data from the 28d follow-up visit post dose 2 are available for subjects in any cohort to inform further clinical development. Also, interim analyses at other timepoints may be prepared.

6 SAMPLE SIZE DETERMINATION

The sample size for each cohort is mainly driven by a telescoping dose escalation study in a limited number of subjects designed for early detection of potential safety and reactogenicity events. The sample size of 16 subjects receiving the vaccine per cohort allow the detection of the most frequent adverse events (AEs) with high probability. For 20 subjects, the probability of detecting at least 1 AE is 88% if the underlying AE rate is 10% and if the AE rate is 15%, then the probability of detecting at least 1 AE is 96%.

7 ANALYSIS SETS AND SUBGROUPS

Data for all subjects will be assessed to determine if they meet the criteria for inclusion in each analysis set. All analysis sets will be assessed and documented prior to releasing the database

7.1 Analysis sets

Screened Set

All subjects who provided informed consent.

Randomized Set

All subjects who have been randomized to IMP.

Safety Set

All subjects who received at least one dose of the IMP.

Page 12 of 36 Version: 3.0 Date: 08 MAY 2024

Analyses of all safety endpoints will be performed using the safety set using the dose level the subject actually received.

Data for all subjects will be assessed to determine if they meet the criteria for inclusion in each analysis set. All analysis sets will be assessed and documented prior to releasing the database.

7.2 Protocol deviations

Protocol deviations are failures to adhere to the inclusion/exclusion criteria and protocol requirements and will be classified into key (important) protocol deviations (PDs) and non-key PDs.

All protocol deviations will be assessed and documented prior to releasing the database.

7.3 Subgroups

There are no planned subgroup analyses.

8 STATISTICAL ANALYSES

8.1 General considerations

In general, all summaries will be displayed by individual vaccine DL and combined placebo. A total group, combining all subjects on placebo and active vaccine, will be presented in addition for accounting (subject disposition), demographics and other baseline characteristics and protocol deviations as applicable unless otherwise specified.

No formal statistical comparisons between vaccine DL of BNT165b1 and placebo will be performed. Missing data, other than that described for partial or missing dates for AEs/concomitant medications/vaccinations (as described below) will not be imputed.

Continuous variables will be summarized using the following descriptive statistics: number of subjects with non-missing data (n), mean, SD, median, minimum (min) and maximum (max).

Categorical variables will be summarized by absolute and relative frequencies (n and %) of subjects in each category and the number of subjects with missing data ('missing' category will be presented if there is one or more missing value).

For event-driven occurrence data (e.g., adverse event, concomitant medication, etc.) percentages will be based on the number of subjects in the analysis set (N). For reported visit data (e.g., lab etc.) percentages will be based on the number of subjects with non-missing values (n).

The rates of binary endpoints such as safety variables (systemic and local reactions) will be provided.

Page 13 of 36 Version: 3.0 Date: 08 MAY 2024

All data collected during the trial will be listed based on safety set unless otherwise specified. The trial day will be presented as appropriate. Listings will be sorted by dose level, site number, subject number, and date of assessment or date of onset (if applicable).

All trial data will be presented at the visit as assigned in the Case Report Form (CRF). No windowing of data for the purposes of assigning to a visit will occur. Unscheduled assessments will not be included in summaries/analysis but will be included in the listings.

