4 TRIAL DESIGN

4.1 Overall design

The BNT165 multi-antigen vaccine clinical development will begin with this FIH clinical trial, a dose escalation multi-center trial designed to assess the safety, tolerability, and exploratory immunogenicity of the vaccine component. The vaccine component assessed in this trial will be BNT165b1, an RNA-LNP encoding for part of *Pf*CSP. Subsequently, multiple other vaccine components will be assessed (either individually or combinations) as well.

BNT165b1 will be evaluated at three DLs to select a safe and tolerable dose in a 3-dose schedule. A sponsor IRC will be used for the BNT165-01 clinical trial.

In total 60 healthy subjects divided into three cohorts by DL will be randomized 4:1 BNT165b1:placebo. Cohort 1 will receive 3 µg doses, Cohort 2 will receive 10 µg or lower doses, and Cohort 3 will receive 30 µg or lower doses.

For a flow diagram summary of the trial, see the schema in Section 1.2. For the planned assessments and visits, see the SoA in Section 1.3. This trial will use a staggered dose escalation schema with sentinel subjects in all cohorts (see Figure 1).

This trial will be initiated with Cohort 1 (3 µg), where two subjects (sentinel group) will be dosed. The randomization will be done at the same clinical site at least 1 hour (h) apart and the two subjects will complete 48 h of follow-up post-Dose 1 (sentinel dosing approach), making sure that at least one subject will receive the vaccine. If the investigator considers the vaccine reactogenicity is acceptable and no stopping/pausing rules are met, 18 more subjects will be dosed. Once these additional 18 subjects complete the 7 d follow-up post-Dose 1, all available clinical, laboratory and other relevant data of these 20 subjects will be reviewed by the IRC. If the IRC considers vaccine reactogenicity is acceptable and no stopping/pausing rules are met, dosing will be opened for the next DL cohort. Subsequent DL cohorts will dose under the same trial rules and will follow the same dose escalation/assessment process.

Provided no cohort trial treatment pausing rules are met throughout the dosing period and the IRC does not determine safety findings judged to be of clinical concern, subjects who received Dose 1 (Day 1) in each DL will proceed to receive Dose 2 (Week 8) and Dose 3 (Week 26). If a pausing rule is met, administration of Dose 2 and/or 3 for the affected and higher DL(s) will be halted, pending IRC review.

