7.1 Discontinuation or pausing (temporary halting) of trial treatment

The following pausing rules are established within the trial based on reported AEs, e-diary reactogenicity data, ECG findings, and clinical laboratory results.

Safety data will be reviewed on ongoing basis by investigators and sponsor.

The sponsor will set up regular IRC meetings (as specified in the IRC Charter). In addition, ad hoc IRC meetings will be triggered by reported events contributing to pausing rules. The IRC may also schedule an ad hoc meeting in absence of any pausing rules being met to evaluate a specific AE/SAE or a safety signal.

The investigator should notify the sponsor within 24 h about any observed Grade 3 AE (Section 7.1.1) or above that is possibly related on an expedited timeline like that of an SAE. A paper form to collect SAE and Grade 3 or 4 AEs contributing to pausing rules will be used for collecting these events.

If the reported events fulfill pausing rules criteria:

- The IRC will review all related data.
- Randomization and trial treatment administration for the impacted DL cohort and any higher DL cohort will be paused until the IRC recommends that assignment to the cohort and administration of trial treatment may be resumed.

For all subjects who are vaccinated, all other routine trial conduct activities, including ongoing data entry, reporting of AEs, subject reactogenicity e-diary completion, blood sample collection, and subject follow-up, will continue during the pause.

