8.5.1 Exposure to IMP

The number and percentage of subjects receiving trial doses will be tabulated by DL for the subjects in safety set.

For each dose, the following will be tabulated:

- Subjects receiving the dose,
- Subjects receiving the complete dose,
- Subjects receiving an incomplete dose,
- Reasons for receiving an incomplete dose,
- For dose 2 and 3 only: reason for not having received the dose.

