- Any missed assessment will be considered as "no reaction". (e.g., if a subject has grade 1 headache on day 1 and 2, missing data on day 3 and 4 and grade 2 headache between day 5 and 7, this should be considered as 2 separate headache events, one of 2 days duration and one of 3 days duration. The maximum duration (3 days in this example) and the maximum severity (grade 2 in this example) would be used for the analysis.).
- For events that persist beyond Day 7, the duration of the reactogenicity event will be derived using the start and the end date of the AE (as recorded on the AE page).
- Onset day, defined as the first day of reporting any severity, will be derived for each recorded local reaction.

A reactogenicity overview summary will include the subjects with

- Any local reaction within 7 days of IMP injection
- Any local reaction that persisted beyond 7 days of IMP injection

Page 20 of 36 Version: 3.0 Date: 08 MAY 2024

Analyses in the overview summary will be provided for reactions of any grade and for reactions of grade ≥3. Analyses will be provided within 7 days of each IMP injections and overall regardless of the number of injections.

The number and percentage of subjects reporting local reactions (pain at the injection site, erythema/redness, induration/swelling) within 7 days after IMP dose will be summarized by maximum severity and cumulatively regardless of the severity. This summary will include categories "Any", "Grade 1", "Grade 2", "Grade 3" and "Grade 4".

All local reaction summaries will be based on the safety set but excluding subjects without any e-diary data throughout the 7 days after vaccination.

In addition, local reactions will also be summarized by:

- Maximum duration (days) of each local reaction after each IMP injection and overall regardless of the number of injections
- Onset day of each local reaction after each IMP injection and overall regardless of the number of injections

For analyses overall across all injections, the subject will only be counted once for each local reaction reported.

Bar charts with the number of subjects for each local reaction throughout 7 days after each dose will be plotted. The bars will be divided into severity categories to highlight the proportions of subjects by maximum severity. In addition, listing of subjects in the safety set with reported local reactions, will be provided.

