8.5.4.1 Overall summary of adverse events

The number and percentage of subjects reporting the below events will be summarized for the subjects in safety set.

- Unsolicited AEs with onset from Day1 through Day 28 post IMP dose will be summarized for each dose (i.e., 1st dose, 2nd dose, 3rd dose) and regardless of the number of doses received. All events entered on the "Adverse Events" eCRF page with an onset date within the above-mentioned timeframe will be analysed. This includes solicited events that persisted beyond Day 7 after IMP administration or that qualified as an SAE. The following will be analysed:
 - Any unsolicited AEs
 - Related AEs
 - AE of grade >=3
 - Related AEs of grade >=3
 - Any solicited reactogenicity event that continues longer than 7 d post-IMP administration or is an SAE
 - Unsolicited AEs leading to withdrawal of IMP
 - Unsolicited AEs leading to study withdrawal
 - SAEs, with onset from Day 1 through Visit 14. The following will be analysed:
 - Any SAEs
 - Related SAEs
 - SAEs of grade >=3
 - Related SAEs of grade >=3
 - MAAE, with onset from Day1 through 28 days after each dose. The following will be analysed:
 - Any MAAEs
 - Related MAAEs

Page 24 of 36 Version: 3.0 Date: 08 MAY 2024

- MAAEs of grade >=3
- Related MAAEs of grade >=3

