8.5.4.2 Adverse event summaries by SOC, PT and grade

The number and percentage of subjects reporting unsolicited AEs occurring up to 28 days post each dose and regardless of the number of doses will be summarized by PT nested within SOC and by grade. AEs with a missing grade will be presented in the summary table with a grade category of "Missing".

Similar analyses will be provided for:

- SAEs (from Day1 through Visit 14)
- SAEs related to IMP (from Day1 through Visit 14)
- AEs related to IMP (from Day 1 through 28 days post each dose and regardless of the number of doses)
- Solicited AEs that continue longer than 7 d post-dose or are a SAE (from Day 1 through 28 days post each dose and regardless of the number of doses)
- MAAEs (from Day 1 through 28 days after each dose)
- Non-serious AEs (from Day 1 through 28 days post each dose and regardless of the number of doses)
- AEs leading to study withdrawal (any such AEs reported during the study)
- AEs leading to IMP discontinuation (any such AEs reported during the study)

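### Per-dose unsolicited AE percentages for Doses 2 and 3 are divided by everyone given at least one dose, so subjects not given that dose count as AE-free after it

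*SAP*

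**What the plan says.** SAP section 8.1 fixes the denominator for event-driven data, naming adverse events: "percentages will be based on the number of subjects in the analysis set (N"). Visit-based data such as laboratory values use the number of subjects with non-missing values instead. SAP section 7.1 defines the Safety Set as "All subjects who received at least one dose of the IMP", and both documents base the safety analyses on it (Protocol section 9.4.2, SAP section 8.5).

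SAP section 8.5.4.1 says that unsolicited AEs "will be summarized for each dose (i.e., 1st dose, 2nd dose, 3rd dose) and regardless of the number of doses received". Section 8.5.4.2 repeats this for the tables by system organ class, preferred term and grade, covering subjects "reporting unsolicited AEs occurring up to 28 days post each dose and regardless of the number of doses". Neither section sets a dose-specific denominator.

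The plan expects that some subjects will not receive every dose. Section 8.5.1 tabulates "For dose 2 and 3 only: reason for not having received the dose", and section 8.2 counts subjects given one, two and three doses. Protocol section 7.4 rules out replacing permanently discontinued subjects.

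The solicited-reaction tables have their own restriction (section 8.5.2.1): they are "based on the safety set but excluding subjects without any e-diary data throughout the 7 days after vaccination".

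**The concern.** The share of subjects with at least one AE in the 28 days after each dose is a primary estimand (Protocol section 3, SAP section 3.1). Its wording does not say whether the denominator is the cohort or those given the dose. The general rule in section 8.1 therefore decides, and it selects everyone given at least one dose.

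A subject who stops after Dose 1 has no post-Dose-2 window. SAP section 8.1.1 defines the day relative to Dose 2 or Dose 3 only from the date of that dose. Non-serious AEs are collected only to 28 days after each dose (Protocol section 8.3.1, SAP section 8.5.4). For this subject, collection ends around Day 29 (Day 1 + 28), and Dose 2 is due on Day 57. The per-dose table would still count the subject as event-free, over a period in which non-serious AEs were not being collected.

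Missed doses may also be uneven across dose levels. If a pausing rule is met, "administration of Dose 2 and/or 3 for the affected and higher DL(s) will be halted, pending IRC review" (Protocol section 4.1), and treatment "will be paused until the IRC recommends that assignment to the cohort and administration of trial treatment may be resumed" (Protocol section 7.1). After a pause, the IRC may recommend permanent discontinuation for a subject, a cohort or the whole trial (Protocol section 7.1.3). Percentages could then differ between dose levels, or between Doses 1, 2 and 3, only because m differs.

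**Working it through.** **The plan's own figures.** The documents state no per-dose AE percentage, so there is no figure on this point to reproduce. The only calculated figures in the statistical sections are the detection probabilities for 20 subjects. They reproduce as 1 − 0.90^20 = 87.8% (stated as 88%) and 1 − 0.85^20 = 96.1% (stated as 96%). They do not bear on this point.

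**Inputs from the documents**

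- Vaccinees per dose level: 16 (Protocol section 4.1.1).
- Combined placebo: 3 cohorts × 4 = 12 (Protocol section 4.1.1; pooling in SAP sections 8.1 and 10.3).
- Denominator for AE percentages: Safety Set N (SAP sections 8.1 and 7.1).

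**Assumed inputs.** The documents give neither the number of missed doses nor AE rates. Every m and x below is an assumption for illustration.

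**Formula.** Let m be the number of subjects given the dose and x the number of those with an AE in the window. Undosed subjects contribute 0 to x, so

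reported rate = x/N = (x/m) × (m/N).

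| Group | N | m | x | Rate among dosed, x/m | Rate as planned, x/N | m/N |
|---|---|---|---|---|---|---|
| One dose level, none missed | 16 | 16 | 8 | 50.0% | 50.0% | 1.000 |
| One dose level, 2 missed | 16 | 14 | 7 | 50.0% | 43.8% | 0.875 |
| One dose level, 4 missed | 16 | 12 | 6 | 50.0% | 37.5% | 0.750 |
| One dose level, 8 missed | 16 | 8 | 4 | 50.0% | 25.0% | 0.500 |
| Combined placebo, 2 missed | 12 | 10 | 5 | 50.0% | 41.7% | 0.833 |

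**Across dose levels.** Suppose one dose level has 8/16 (50.0%) and another, where 4 subjects missed the dose, has 8/12 (66.7%). Both print as 8/16 = 50.0%.

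**Against sampling error.** Exact (Clopper-Pearson) 95% intervals are wide at this size: 24.7% to 75.3% for 8/16; 23.0% to 77.0% for 7/14 against 19.8% to 70.1% for 7/16; and 21.1% to 78.9% for 6/12 against 15.2% to 64.6% for 6/16. The shifts are smaller than this uncertainty, but they always go downwards.

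**Not affected.** Every Safety Set member has had Dose 1, so the Dose 1 percentages are correct. So are the summaries regardless of the number of doses and the SAE summaries, which run from Day 1 to Visit 14.

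**The case against.** The strongest reply is that x/N is a legitimate quantity: the share of the treated cohort that goes on to have an AE after Dose 2 or 3. The estimand is introduced as being for each dose-level cohort, which fits that reading. On it, 8/16 in both dose levels is simply correct. The alternative, x/m, is conditional on receiving the dose and so is open to selection. The reply has force, but the collection windows count against it. For undosed subjects non-serious AEs are not collected in the relevant period, so x/N treats unobserved subjects as observed and event-free. If the cohort-wide quantity is what is wanted, the plan should say so.

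Several other points stand and limit the weight of the concern:

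- The error is zero if everyone receives every dose, and its size otherwise is unknown.
- No hypothesis is tested, and the pausing rules count events, not percentages.
- Escalation rests on the 7-day review after Dose 1, which this does not touch.
- Section 8.5.1 tabulates the number given each dose, so a reader can recompute x/m.
- The two pausing passages describe temporary halts. A lasting omission for a cohort needs the permanent discontinuation in Protocol section 7.1.3.
- The solicited-reaction exclusion depends on diary data, not on dosing. The two sets of per-dose rates are on different bases now, and the fix would bring them closer without making them identical.
- Section 8.5.4.1 calls explicitly for each dose separately only for unsolicited AEs. Whether MAAEs will be split by dose is unclear.

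**Conclusion.** The concern holds. SAP sections 7.1, 8.1, 8.5.4.1 and 8.5.4.2, read together, divide the Dose 2 and Dose 3 unsolicited AE counts by all subjects given at least one dose, and no other section overrides this. The dilution factor is exactly m/N. With 16 vaccinees, 2 or 4 missed doses would turn a 50.0% rate among dosed subjects into 43.8% or 37.5%; those counts are assumptions. The bias only ever understates the rate among dosed subjects, and it can differ between dose levels.

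This should be fixed because it affects how a primary estimand is reported. It does not threaten the trial's conduct or its escalation decisions. The text and the arithmetic are certain. The size in practice, and whether MAAEs are affected, are not.

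**What to change.** Add to SAP sections 8.1 and 8.5.4: *For unsolicited AE summaries by dose (and MAAE summaries, if presented by dose), percentages are based on Safety Set subjects who received that dose, with this number shown in the column header; summaries regardless of dose use the Safety Set N.* State in section 8.5.4.1 whether MAAEs are presented by dose.

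The cost is one sentence and some column-header programming. The drawback is that denominators will differ between doses, and the later-dose rates describe only those who went on to receive that dose. Comparisons across doses therefore remain open to selection. The change removes the arithmetic dilution, not the selection.
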